#### **3.2 SECONDARY OBJECTIVES**

There are four secondary objectives.

- To compare observed RFSs for the study population with the predicted RFSs for the study population. The predicted RFS values will be calculated from each patient's clinical and pathologic data by standard algorithms (Duke and CaPSURE). The observed and predicted RFSs will be presented as Kaplan-Meier plots and comparisons will be performed using the logrank test.
- To compare the observed RFS with the RFSs of a historical comparison group of MUSC prostatectomy patients. These patients will be matched to the experimental group for race, Gleason score, and pathological stage. The observed, historical RFSs will be presented as Kaplan-Meier plots and comparisons will be performed using the logrank test.
- To describe associations between the RFS values and various immunologic, genetic, and biochemical parameters on research blood and tissue specimens.
- To describe the toxicity of PROSTVAC-V/F in this patient population.

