## 4 INVESTIGATIONAL PLAN

### 4.1 STUDY DESIGN AND DURATION

This will be a Phase II study of adjuvant PROSTVAC-V/F in subjects at high risk for relapse after radical prostatectomy. The study will be carried out at MUSC and the VAMC. The coordinating center will be at the Sponsor-Investigator Support Unit. Additional sites may be recruited as needed to ensure accrual.

We anticipate a two year period of accrual and an equal period of follow up for each subjects, or approximately four years total, from the point of completions of approvals and contracts.

The study population will be post-prostatectomy patients whose pathology reports documents one or more high risk features, including one or more of the following: pT3b or pT4, pN1, pT3a (without adjuvant radiation), positive margins, pre-operative PSA  $\geq 10$  ng/mL, Gleason score 8-10. Each site PI will be responsible for reviewing all prostatectomy cases to determine the patient's eligibility and interest in participating in the study.

Forty evaluable subjects (total 44 subjects) will be enrolled. Subjects will be treated with PROSTVAC-V/F alone. Subjects will be followed for relapse for two years after prostatectomy.

Prior to any study specific activities, the patient must be aware of the nature of his/her disease and willingly consent to the study after being informed of study procedures, the experimental therapy, possible alternatives, risks and potential benefits. IRB approval of this protocol and accompanying consent is required.

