**Sample Size Justification:** To estimate the likelihood of RFS at 2 years for subjects at high risk of relapse, we extracted data from two sources. The first source is a database of high risk subjects that we have previously used in published research (122). The database contains clinical synopses of 243 subjects treated with radical prostatectomy (retropubic, laparoscopic, and perineal) for high-risk prostate cancer. These subjects were treated by multiple surgeons at several academic medical centers. None received any adjuvant therapy. High-risk features included one or more of the following criteria: pre-operative PSA  $\geq$  10 ng/mL; Gleason score 8-10; positive surgical margins, seminal vesicles, extraprostatic extension, or lymph nodes; persistently detectable PSA  $>45$  days after surgery. Relapse-free survival was defined as the interval (days) from prostatectomy to the first of the following: a) PSA of  $\geq$  0.2 ng/mL (confirmed)

>30 days later, b) appearance of lesions consistent with metastases on imaging studies, or c) institution of new prostate cancer therapy. The observed 1yr probability of RFS was 0.751 and the 2yr probability of RFS was 0.645.

An additional source of data for RFS was the ECOG E3886 study (13), in which subjects with node-positive prostate cancer after radical prostatectomy (n = 98) were randomized to immediate ADT, or ADT at the time of clinical relapse. This analysis was performed by [name] (ECOG statistical office) at our request, in 2010. Relapse was defined as the first of the following: a) the appearance of local or distant metastases identified by imaging or physical examination, b) the first increase in PSA  $> 0.1$  ng/mL following a post-prostatectomy PSA nadir of  $< 0.1$  ng/mL or c) death from any cause. The RFS probability curve is shown in Appendix B. The observed 1yr probability of RFS was 0.73 and the 2yr probability of RFS was 0.56.

While the two groups differ somewhat in the disease status of the subjects, as well as frequency and manner of follow up, the probabilities of RFS agree quite closely. For the purposes of our power analysis and sample size, we will assume that the true probability of RFS at 2 years, for patients similar to our proposed study population, is 0.60.

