We define an “interesting” reduction in the risk of relapse to be 30% (i.e., increase in the probability of RFS from 0.6 to 0.78). Assuming a one-sided alpha = 0.1, with 30 evaluable patients, we have 80% power to detect this difference based on an exact binomial test. Thus if among 30 evaluable subjects, at least 24 are recurrence free at 24 months, we will reject the null hypothesis (2 year RFS=0.60) and conclude that the PROSTVAC intervention improves RFS relative to the current standard of care in this patient population (one-sided p-value  $\leq 0.025$ ). Anticipating a final sample size of 30 patients with 10% drop out rate, we plan to enroll 33 patients for this study.

**Interim Analysis:** An interim analysis for futility will be performed through Simon’s minimax two-stage design (Simon, 1989) when a total number of 19 patients are evaluable. The design is described as follows:

**Stopping criteria:** Stop the study if there are 11 or fewer recurrence free among the first 19 evaluable patients. Otherwise, additional patients will be accrued resulting in a total evaluable sample size of 30.

**Decision rule at N=30 evaluable patients:** Reject the null hypothesis if there are 22 or more recurrence free among the 30 evaluable patients. We claim that the PROSTVAC intervention improves RFS relative to the current standard of care in this patient population. This design controls the type I error rate at 0.1 and yields the power of 0.8.

**Safety Monitoring:** Continuous safety monitoring will be performed with early stopping rules in the case of unacceptable risk to the subjects, defined as evidence in favor of a risk of a grade 3 or greater toxicity deemed to be possibly related to treated of 25% vs. an acceptable rate of 10%. Stopping criteria are shown in the table below. The stopping rules are based on a likelihood ratio. Specifically, the likelihood ratio is calculated based on a hypothesized 10% event rate (safe) vs, a 25% event rate (unsafe) and likelihood ratios in excess of 8 (in favor of an event rate of 25%)

are considered sufficient evidence to stop the trial. For example, 7 events in 33 patients yields an event rate of 0.21, which has a likelihood ratio of 9.21 favoring a rate of 25% vs. 10%.

Stop if:	Likelihood Ratio	Observed Event Rate
3 events in $\leq 6$ patients	$\geq 9.04$	$\geq 0.50$
4 events in $\leq 12$ patients	$\geq 9.08$	$\geq 0.33$
5 events in $\leq 18$ patients	$\geq 9.13$	$\geq 0.28$

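### The MUSC historical controls are matched on race, Gleason score and pathological stage, but the named log-rank test ignores those factors; if they predict relapse, the test is conservative and loses some power.

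*Combined protocol and SAP*

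**What the plan says.** The second secondary objective in Section 3.2 is "To compare the observed RFS with the RFSs of a historical comparison group of MUSC prostatectomy patients". It continues: "These patients will be matched to the experimental group for race, Gleason score, and pathological stage". The analysis is then given as "The observed, historical RFSs will be presented as Kaplan-Meier plots and comparisons will be performed using the logrank test".

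Nothing else in the document refines this. Section 10.2 covers the comparison with nomogram-predicted RFS (10.2.1), toxicity (10.2.2) and laboratory correlates (10.2.3). The synopsis does not list the MUSC comparison at all. The plan does not say whether matching is individual or by frequency, how many controls there are per trial man, how Gleason and stage are grouped, or what alpha and sidedness apply. The only test alpha in Section 10.1 belongs to the primary analysis: "Assuming a one-sided alpha = 0.1, with 30 evaluable patients, we have 80% power to detect this difference based on an exact binomial test".

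The word log-rank is unlikely to carry an implied stratification. Section 3.2 describes the unmatched nomogram comparison in the same terms, and Section 2.4.3 says stratified when reporting the log-rank result of an earlier randomized trial.

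**The concern.** Matching makes the two cohorts alike in their mix of risk groups. Differences in relapse between risk groups then largely cancel in the observed-minus-expected count, so that count varies less from one study to the next than it would for two independently drawn samples. The unstratified log-rank variance still allows for the between-group variation. It is therefore too large and the test statistic too small.

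The plan itself treats two of the three factors as prognostic. Gleason 8–10 and pT3b or pT4 are high-risk entry criteria in Section 4.3, and T3/T4 disease is listed among the features of relapse risk in Section 2.2.1. Eligibility is also broad enough for both to vary, because positive margins or a pre-operative PSA of at least 10 ng/mL suffices alone.

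The stake is precision in a small secondary comparison. The matching is meant to improve comparability and precision, and the named test does not use the precision.

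**Working it through.** **Plan figures.** No power, alpha or number of controls is stated for this comparison. The nearest stated figure is the primary two-stage rule in Section 10.1 (stop at 11 or fewer of 19; reject at 22 or more of 30). The exact binomial sum gives type I error 0.093 and power 0.801, which agrees with the stated 0.1 and 0.8. That rule does not govern the MUSC comparison.

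**Inputs from the plan**
- Trial men: 30, from Section 10.1 ("Anticipating a final sample size of 30 patients with 10% drop out rate, we plan to enroll 33 patients for this study"). Section 4.1 differs ("Forty evaluable subjects (total 44 subjects) will be enrolled"); 30 is used because the power statement uses it.
- Control 2-year RFS: "we will assume that the true probability of RFS at 2 years, for patients similar to our proposed study population, is 0.60".
- Effect: "increase in the probability of RFS from 0.6 to 0.78". The marginal hazard ratio under proportional hazards is ln 0.78 / ln 0.60 = 0.2485/0.5108 = 0.486.
- Follow-up: two years from surgery.

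**Assumed, because the plan is silent**
- Two-sided 5%; one or three controls per man.
- Binary race, Gleason and stage with prevalences 0.5, 0.4 and 0.35; race hazard ratio 1.2; Gleason and stage hazard ratios each 2 or each 3.

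**Baseline power.** At 1:1, expected relapses are 30 × 0.40 + 30 × 0.22 = 18.6. The Schoenfeld formula gives √(18.6 × 0.25) × |ln 0.486| − 1.96 = 1.55 − 1.96 = −0.41, so power is about 34%. The comparison is weak before any question of matching arises.

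**Spread implied by the assumptions.** The variance of the log hazard is the sum of p(1 − p)(ln HR)².
- Hazard ratio 2: 0.25 × 0.033 + 0.24 × 0.480 + 0.2275 × 0.480 = 0.233, SD 0.48.
- Hazard ratio 3: 0.25 × 0.033 + 0.24 × 1.207 + 0.2275 × 1.207 = 0.573, SD 0.76.

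For exponential times the log-time variance within a group is π²/6 = 1.645. The within-match correlations are therefore 0.233/1.878 = 0.12 and 0.573/2.218 = 0.26.

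**Simulation 1.** Exponential RFS, exact matching at 1:1, censoring at two years, marginal RFS held at 0.60 and 0.78. Ranges cover repeated runs.

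| Gleason and stage HR | Size, plain | Size, stratified | Power, plain | Power, stratified |
|---|---|---|---|---|
| 2 each | 3.9–4.2% | 4.9–5.2% | 33% | 35% |
| 3 each | 2.1–3.0% | 4.7–4.8% | 33% | 40% |

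At 1:3 and hazard ratio 3, power is 42% plain against 51% stratified. With 1,500 runs, the Monte Carlo standard error near 33% power is √(0.33 × 0.67/1500) = 1.2 points, so the 2-point gap at hazard ratio 2 is small beside the noise.

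**Simulation 2.** A different model: 18 matching cells (2 race × 3 Gleason × 3 stage), with the between-cell SD of the log hazard varied.

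| SD | Size 1:1, plain / stratified | Power 1:1, plain / stratified | Power 1:3, plain / stratified |
|---|---|---|---|
| 0 | 5.5 / 4.9% | 34 / 32% | 39 / 38% |
| 0.5 | 4.0 / 4.8% | 32 / 33% | 40 / 43% |
| 1.0 | 2.4 / 5.1% | 33 / 39% | 41 / 54% |

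The two models agree: hazard ratio 2 (SD 0.48) sits on the 0.5 row, and hazard ratio 3 (SD 0.76) lies between the last two rows. In both models the mechanism is balance across groups, so frequency matching produces the same effect. Stratifying by individual pair at 1:1 gives power of 29% at SD 0.5, below the plain test's 32%.

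**Separate bias.** Suppose only the trial men cannot relapse in the first 120 days. In the 18-cell model the 1:1 size becomes 8.6% plain and 8.5% stratified at SD 0, 7.3% and 9.0% at SD 0.5, and 3.9% and 10.7% at SD 1.0.

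**The case against.** The strongest objection is that conservatism is conditional and may not be the net effect. Trial men must have a post-operative PSA below 0.2 ng/mL by day 120 (Section 4.3), and their PSA relapse counts only after all vaccine doses (Section 7.5), while RFS runs from surgery. Nothing says the MUSC controls meet either condition. If they do not, the plain test can exceed its level, and stratifying alone makes that worse. This stands. It is a bias in the comparison and does not make the unstratified variance right, but the fix has to deal with both.

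Other points also stand. A reader might infer that controls are individually matched; Section 3.2 fits frequency matching equally well. A reader might infer a nominal 5% level; none is set for this test. A reader might take a within-pair correlation of 0.5, at which plain size falls to 1.3%. Nothing in the documents supports it, and it would need Gleason and stage hazard ratios of about 6.5 each.

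A stratified hazard ratio also differs from the marginal one that corresponds to the Kaplan-Meier plots. That is a difference of estimand and not an error in the plan, which names no hazard ratio for this comparison.

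Finally, the bullet in Section 3.2 is short, and the silence of Section 10.2 may be simple under-specification. Even so, the only method named is the unqualified test, and naming a better one costs a sentence.

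**Conclusion.** The point holds conditionally and is minor. The plan matches on factors that it treats elsewhere as prognostic and then names a test that ignores them. If those factors predict relapse and the cohorts are otherwise comparable, the test is conservative relative to whatever alpha is chosen.

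At the assumed two-sided 5% with 30 trial men, and Gleason and stage each at a hazard ratio of 2 to 3, size is about 4% falling to 2–3%, against about 5% stratified. The power loss is about 2 to 6–7 points at 1:1 and about 3 to 10 points at 1:3. It is near nil if the factors are weakly prognostic. Power at 1:1 stays at or below about 40% under these assumptions whichever test is used.

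The documents do not support the unconditional statement that the test runs below 5%. Nor do they support any effect on the trial's main conclusion, which rests on the binomial rule in Section 10.1.

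**What to change.** In Section 3.2, and in a new paragraph of Section 10.2, specify the MUSC comparison along these lines: *RFS in the trial cohort and the matched MUSC controls will be compared by a log-rank test stratified by race, Gleason group and pathological stage group, at a stated alpha and sidedness; any hazard ratio will come from a Cox model with the same strata.* Keep the Kaplan-Meier plots. Do not stratify by individual pair, which can lose power at 1:1.

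In the same paragraph, state the matching method and ratio, and apply the trial's post-operative PSA entry condition and relapse definition to the controls. Controls receive no vaccine, so say how the rule that PSA relapse counts only after dosing carries over to them. Stratification does not remove this bias.

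The cost is a short paragraph. Section 10.5 already records the matching factors for trial men, and they must be known for controls in order to match. Groups need to be coarse, because a stratum with men from only one cohort adds no information. If the factors do not predict relapse, stratifying by all 18 cells costs about 2 points of power at 1:1 (32% against 34%).

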#### 4.3 INCLUSION CRITERIA

1. Age  $\geq 21$
2. Completed radical prostatectomy for pathologically-verified adenocarcinoma of the prostate no more than 120 days prior to start of treatment. The following procedures are acceptable: radical retropubic prostatectomy (RRP), laparoscopic radical prostatectomy (with or without robotic assistance; LAPD), radical perineal prostatectomy (RPP).
3. Post-operative PSA  $< 0.2$  ng/mL by 120 days after prostatectomy
4. Must have one or more of the following:
  - pT3b or pT4 primary tumor
  - Gleason score 8-10
  - pN1 lymph node disease
  - positive surgical margins
  - pre-operative PSA of  $\geq 10$  ng/mL
  - presence of any tertiary Gleason 5 component on the prostatectomy pathology report.

**Note:** Patients with pT3a disease who lack one of the above criteria, and who refuse adjuvant radiation, may also be enrolled.

5. ECOG performance status 0-1
6. Adequate hematologic, renal, liver function per parameters in Table 1
7. Subject of fathering potential must agree to use an adequate method of contraception to avoid conception throughout the study and for at least 4 weeks after the last dose of study drug to minimize the risk of pregnancy.
8. Subjects must have had a negative bone scan, and CT of abdomen and pelvis within 26 weeks prior to registration. Additional forms of imaging (Prostascint scan, MRI) may be substituted for a CT scan of the abdomen and pelvis if clinically indicated.

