#### 4.4 EXCLUSION CRITERIA

1. Pure small cell carcinoma of the prostate
2. Radiographically-demonstrable metastases at any time prior to the time of enrollment

3. Diagnosis of cancer requiring systemic therapy in the past 5 years
4. Presence of any major medical condition which, in the opinion of the investigator, precludes participation in the study
5. Neoadjuvant or adjuvant therapy of any kind
6. Chronic administration (defined as daily or every other day for continued use > 14 days) of systemic glucocorticoids within 28 days of the first planned dose of PROSTVAC-V/F. Use of inhaled steroids, nasal sprays, and all topical preparations (creams, solutions, gels, ointments, etc.) for up to 5% of the body surface area is allowed.
7. Use of systemic immunosuppressant agents including anti-metabolites, glucocorticoids, TNF $\alpha$  antagonists, antibodies to IL6 or IL6R, calcineurin inhibitors, mTOR antagonists
8. Prior history of serious toxicity or a systemic reaction to vaccinia immunization such as myopericarditis progressive vaccinia infection, or eczema vaccinatum.
9. Inflammatory or exfoliative skin diseases such as eczema, psoriasis that disrupt epidermis
10. Active infections requiring systemic therapy
11. Serologic evidence of HIV/AIDS.
12. Positive hepatitis C serology or active hepatitis B infection.
13. History of allergy to eggs, egg products, aminoglycoside antibiotics
14. History of myocardial disease, such as myocarditis, cardiomyopathy, congestive heart failure, ischemic cardiomyopathy
15. Prior solid organ or stem cell transplant
16. History of or active autoimmune disease (e.g., autoimmune neutropenia, thrombocytopenia, or hemolytic anemia, systemic lupus, localized lupus, Sjogren's syndrome, scleroderma, myasthenia gravis, Goodpasture's syndrome, or Addison's disease). Persons with vitiligo, Hashimoto's thyroiditis, or Graves disease are not excluded.
17. Vaccination with live attenuated vaccine within 28 days prior to day 1 of PROSTVAC-V/F administration or vaccination with a killed vaccine within 14 days prior to day 1 of PROSTVAC-V/F.

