## 5 **TREATMENTS**

### 5.1 STUDY TREATMENT: PROSTVAC-V/F

Subjects must start study drug within 120 days after surgery.

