## 7.5 EFFICACY ASSESSMENTS

Efficacy assessments will primarily be performed by measurement of PSA and by physical assessment. Imaging studies (CT scans of the abdomen and pelvis, and bone scans) will be performed at baseline (up to 16 weeks prior to treatment) and at the end of the study (or within the preceding 2 months before end of study). Otherwise, scans will be performed only if clinically indicated for evaluation of relapse or off study. Additional forms of imaging (Prostascint scan, MRI) may be substituted for a CT scan of the abdomen and pelvis if clinically indicated. However, the imaging method used at baseline will be used for follow up scans. Compliance with therapy may be considered a component of the efficacy assessment. Compliance with PROSTVAC-V/F will be monitored at each visit by interviewing the patient and reviewing the infusion center records for administration.

Both primary and secondary efficacy assessment involve measurement of RFS. Recurrence will be defined as the occurrence of any of the following:

- Institution of new prostate cancer therapy
- First detection of a PSA level  $\geq 0.2$  ng/mL (confirmed  $> 30$  days later) after completion of all PROSTVAC V/F vaccine doses
- Development of radiographically-demonstrable metastases
- Death

RFS at two years will be met if a patient has met none of the above criteria two years post-surgery. RFS as a time to event endpoint will be measured as the time in days from surgery to any of the above conditions being met.

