## 10.2 SECONDARY OBJECTIVES

### 10.2.1 Comparison of Observed RFS with Predicted RFS

A secondary endpoint will be a comparison of the observed RFSs with the predicted (“virtual”) RFS for the same patients based on clinical and pathologic information collected at baseline. The predicted RFSs will be constructed with published and validated algorithms (Duke and CaPSURE). The observed RFSs of the treated subjects are compared with the predicted RFSs as if the same subjects had not been treated. The comparison is performed using the logrank test of the observed and predicted RFSs. These represent the estimated RFSs for patients with those clinical characteristics if they did not receive any adjuvant therapy.

RFSs will be displayed graphically using Kaplan-Meier curves. We then use the log rank test to compare the virtual or estimated RFSs values of the test patients with the observed values following PROSTVAC-V/F.

The comparative analysis (observed vs predicted RFS) will be performed repeatedly during the course of the study, whenever an additional 5 subjects relapse or reach the end of the 2-year follow up period.

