- j. If available: Send 5 thin (5 micron) sections on glass for H+E and IHC staining. These can be sent at any time after consent has been signed.
- k. Lipid panel requires patients to be fasting and can be done any time after informed consent is signed and prior to day 1 agent administration.
- l. HIV, Hep B and Hep C serology screening, unless known negative within previous 2 years prior to registration.
- m. PSA confirming eligibility can be done outside of the 30 day window. However, if PSA confirming eligibility was done greater than 30 days prior to day 1, it should be repeated prior to day 1 agent administration to ensure PSA is < 0.2ng/mL
- n. Day 1 assessments completed within 24 hours of screening assessments do not need to be repeated.
- o. Interim medical history includes any changes to the patient's medical history and/or any clinical changes since the previous clinic visit.
- p. For non-local patients in follow up, all attempts should be made to have subject return to the clinic for all follow up visits, but specifically day 225 and day 703. However, clinical care procedures (PSA, CMP, CBCD, focused physical exam and interim medical history – to include AE assessment and conmed assessment) may be done locally and the records provided. At a minimum, a PSA must be done and results provided to the study team. If a clinic visit is not done during follow up, the study team may conduct a phone interview (using the phone contact guide, Appendix D) in lieu of an clinic visit to assess adverse events, current cancer therapy and PSA level. Quality of life surveys may also be conducted over the phone by the study team if the subject does not return to clinic.
- q. Questionnaires may be mailed to the subject in pre-metered envelope if they are unable to come into the clinic to complete them (ie: due to COVID19 travel restrictions). The subject will complete the questionnaires at home and then mail the completed questionnaires back to the main site in the provided envelope.

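### The secondary log-rank comparisons count trial men at risk from surgery although they must be relapse-free at entry up to 120 days later, and no delayed entry or landmark is stated

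*Combined protocol and SAP*

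**What the plan says.** **Time origin.** Section 7.5: "RFS as a time to event endpoint will be measured as the time in days from surgery". The synopsis agrees.

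**Entry.** Section 4.3 allows "Completed radical prostatectomy for pathologically-verified adenocarcinoma of the prostate no more than 120 days prior to start of treatment", and section 5.1 repeats the limit: "Subjects must start study drug within 120 days after surgery". Section 4.3 also requires a post-operative PSA below 0.2 ng/mL. If the qualifying PSA is more than 30 days old at day 1, Appendix A note m says "it should be repeated prior to day 1 agent administration to ensure PSA is < 0.2ng/mL". Section 4.4 excludes "Radiographically-demonstrable metastases at any time prior to the time of enrollment" and "Neoadjuvant or adjuvant therapy of any kind".

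**Comparisons.** Section 10.2.1, for the nomogram predictions: "The comparison is performed using the logrank test of the observed and predicted RFSs". Section 7.5.2 says the same. Section 3.2, for MUSC prostatectomy patients matched on race, Gleason score and pathological stage: "The observed, historical RFSs will be presented as Kaplan-Meier plots and comparisons will be performed using the logrank test". The MUSC comparison appears only in 3.2; neither the synopsis nor section 10.2 describes it.

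None of these sections mentions delayed entry, a landmark, or a requirement that comparators be relapse-free at a corresponding time.

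**The concern.** Relapse in section 7.5 means new prostate cancer therapy, confirmed PSA of at least 0.2 ng/mL, radiographic metastases, or death. A man who had met any of these before his first dose would, in essence, not be in the trial. The interval from surgery to first dose is therefore immortal time, yet an ordinary Kaplan-Meier curve and log-rank test count him as at risk throughout it.

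A MUSC control followed from surgery can fail in that interval. Race, Gleason score and stage do not screen out such men. The result is an early separation of the curves produced by the entry rule, always in the vaccine's favour.

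These are the plan's only time-to-event comparisons of treated with untreated experience. Section 10.2.1 also repeats the predicted-curve test each time five more subjects relapse or complete follow-up, so a biased result would be seen several times.

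**Working it through.** **The plan's own figures.** The plan gives no error rate or power for either log-rank test, so there is none to reproduce. The operating characteristics it does state, for the primary two-stage rule (11/19, then 22/30; 0.60 vs 0.78), reproduce: type I error 0.093 and power 0.801, against a stated 0.1 and 0.8.

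**Inputs from section 10.1.** RFS at 1 and 2 years is 0.751 and 0.645 in the 243-man database, and 0.73 and 0.56 in the node-positive trial series (n = 98).

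**Assumptions.** The vaccine is inert. Hazard is constant within each year and runs from day 0. Follow-up ends at day 730. A trial man enters on day d and has no event before it. The documents give no distribution of d; days 45, 82.5 and 120 are illustrative.

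**Formulas.**
- Cumulative hazard at entry: H(d) = -ln S(1 yr) × d/365, and S(d) = exp(-H(d)).
- Trial men's 2-year RFS: Sc = S(730)/S(d).
- Apparent cut in 2-year relapse risk: 1 - (1 - Sc)/(1 - S(730)).
- Observed events per man: 1 - Sc. Expected events when time is counted from surgery: H(d) + (1 - Sc). So O/E = (1 - Sc)/[H(d) + (1 - Sc)].

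**Worked case, 243-man rates, d = 120.** H = 0.2863 × 120/365 = 0.0941; S(120) = 0.910; Sc = 0.645/0.910 = 0.709. Risk cut = 1 - 0.291/0.355 = about 18%. O/E = 0.291/(0.0941 + 0.291) = 0.756.

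| Control rates | d | H(d) | Sc | 2-year risk cut | O/E | Large-sample HR, equal arms |
|---|---|---|---|---|---|---|
| 0.751/0.645 | 45 | 0.035 | 0.668 | 6.5% | 0.904 | 0.903 |
| 0.751/0.645 | 82.5 | 0.065 | 0.688 | 12.1% | 0.828 | 0.826 |
| 0.751/0.645 | 120 | 0.094 | 0.709 | 17.9% | 0.756 | 0.752 |
| 0.73/0.56 | 45 | 0.039 | 0.582 | 5.0% | 0.915 | 0.914 |
| 0.73/0.56 | 82.5 | 0.071 | 0.601 | 9.4% | 0.849 | 0.846 |
| 0.73/0.56 | 120 | 0.104 | 0.621 | 13.9% | 0.786 | 0.782 |

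The HR column runs from 0.914 to 0.752, an apparent hazard reduction of about 9-25%.

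**With delayed entry.** Expected hazard then accrues only after d. Expected events become 1 - Sc, the same as observed, and O/E = 1.00.

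**Error rate, MUSC-type comparison.** This was simulated with 30 vs 30 independent men and the 243-man rates. The level, one-sided 2.5%, is illustrative because the plan states none. False superiority was 4.1-4.3% if all enter at day 45, about 6-7% for entry uniform over days 45-120, and 8.2-8.7% if all enter at day 120. With delayed entry it returned to 2.4-2.8%.

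**Sensitivity, 243-man rates.** Entry uniform over days 21-120 gives O/E 0.85; over days 30-90 it gives 0.87. If comparator relapses are not recorded before day 45 (same 1- and 2-year rates, entry 45-120), O/E is 0.91, the 2-year risk cut is 6%, and false superiority is 4.0%.

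**The case against.** **The size is not fixed by the documents.** A reader might infer one figure, such as a 17% cut in relapse. That is a mid-window hazard-scale value (O/E 0.83), and it depends on assumed entry days and hazard shape. On the 2-year risk scale the mid-window figure is about 9-12%. Day 45 is not an entry rule either: section 7.1 asks for a PSA at 45 days or later only if the nadir was not below 0.2 before then, so earlier entry is possible. If early comparator relapses go unrecorded, the bias shrinks further. Persistently detectable PSA, which the 243-man series counted as a high-risk feature, could enlarge it. This objection stands, and only a conditional range is supported.

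**The predicted curves may already be conditioned.** A reader might infer that both comparators certainly include failures before entry. The documents do not say what the Duke and CaPSURE algorithms condition on. Predictions use baseline clinical and pathologic data (10.2.1), and post-operative PSA is among the recorded parameters (10.5). This stands. For MUSC the listed matching factors point clearly to exposure, although 3.2 gives no control eligibility rules.

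**The error rates do not carry over to the predicted-curve test.** Observed and predicted RFS concern the same men, so an independent-sample simulation can speak only to the MUSC comparison. This stands.

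**The tests are secondary.** The efficacy decision is binomial, and section 10.1 keeps time-to-event RFS out of the primary inference. This limits the importance of the point but does not remove the bias.

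**Conclusion.** The concern holds in conditional form. The MUSC comparison is biased toward the vaccine on the stated matching factors. The predicted-curve comparison is biased too, unless the algorithms already condition on an undetectable post-operative PSA. With the protocol's control rates, hazard from day 0 and entry at days 45-120, an inert vaccine would show a relapse hazard roughly 9-25% lower and a 2-year relapse risk about 5-18% lower. Earlier entry, or unrecorded early relapses in comparators, would reduce this. False superiority of about 4-9% applies only to a 30 vs 30 MUSC log-rank at an illustrative one-sided 2.5%.

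The point concerns the risk sets of the secondary tests. It should not be read as a finding on the primary binomial test: whether 0.60 is the right null is a separate question, and changing it would not repair these comparisons. Because the tests are secondary and the repair is cheap, the change should be made, but the primary decision rule does not depend on it.

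**What to change.** In sections 3.2, 7.5.2 and 10.2.1:

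- Keep surgery as time zero, but let each trial man join the risk set on his first-dose date in these Kaplan-Meier and log-rank analyses.
- Count each MUSC control from a matched number of days after surgery, and include him only if he is relapse-free with PSA <0.2 ng/mL at that point.
- State what each nomogram's prediction conditions on. Use S(t)/S(entry) only where the algorithm does not already condition on an undetectable post-operative PSA; applying it otherwise would over-correct.
- Add the MUSC comparison to section 10.2 so that its rules are written in the statistical section.

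**Cost.** A few sentences of wording. Surgery and first-dose dates suffice for trial men; MUSC controls need their dated PSA and relapse records. Some MUSC men will drop out, and the comparison will look slightly less favourable. No visit, dose or sample size changes.

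**What remains.** Section 7.5 counts PSA relapse only after all doses are completed. That separate delay is not removed by entry at first dose. It is small: O/E is about 0.98 if every relapse is a PSA event recorded at the last dose.
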